4.5.1.1 Liver Chemistry Stopping Criteria

Discontinuation of study drug for abnormal liver tests is required by the Investigator when a subject meets one of the conditions outlined below. The Investigator can discontinue study drug in the presence of abnormal liver chemistries not meeting protocol-specified stopping rules if they believe that it is in best interest of the subject.

- Alanine aminotransferase (ALT) or aspartate aminotransferase (AST) $\geq 3 \times$ upper limit of normal (ULN)
 - if there is an elevation of $>2 \times$ ULN, the laboratory assessment should be repeated
 - If ALT or AST is $\geq 3 \times$ ULN, international normalized ratio (INR) should be tested

- If a subject is discontinued from the study because of ALT or AST $\geq 3 \times$ ULN, every reasonable attempt should be made to follow the subject until the value(s) normalize or until the Investigator deems it to be chronic or stable.
- Total bilirubin (TBL) $\geq 1.5 \times$ ULN
- Creatine kinase (CK)/creatine phosphokinase (CPK) $\geq 5 \times$ ULN for more than 1 week

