 - A urine drug screen will test for controlled substances at Screening, Baseline Pain Assessment Period, and at Week 4/EOT/ET. A dipstick urine drug screen will be performed at Baseline (Week 0) for rapid detection of controlled substances and for certain prescription medications in order to determine if the subject continues to meet subject eligibility. The following controlled substances will be tested for with a urine drug screen and/or urine dipstick according to the schedule presented in Table 6-1: amphetamine, barbiturates, benzodiazepines, buprenorphine, cocaine, ecstasy (MDMA), methadone, morphine/opiates, methamphetamine, marijuana (THC), phencyclidine (PCP), propoxyphene, tricyclic antidepressants. Negative drug screens are required for study eligibility.
 - If there is a positive urine drug screen for an analgesic medication that is not allowed per protocol, the subject must washout of medication, if appropriate, prior to the Baseline Pain Assessment Period.
 - If there is a positive urine drug screen for a medication that is allowed per protocol (e.g., metformin leading to a false positive for amphetamine), the subject must have a valid prescription for such medication, and if the subject denies use of the positive prohibited medication (e.g., amphetamine), they can be included in the study and it will not be considered a protocol deviation.

Laboratory evaluations will be completed according to the schedule presented in [Table 6-1](#) and procedures detailed in the study laboratory manual. Additional safety testing may be performed at the discretion of the Investigator or designee.

Table 6–1 Safety Laboratory Evaluations

Visit	Tests
Screening	CHEM, CBC, UA, COVID-19 ^a , serum pregnancy, and urine drug screen
Baseline Pain Assessment Period	Urine drug screen
Baseline (Week 0) predose	CHEM, CBC, UA, urine pregnancy, and urine dipstick test ^b
Day 3	CHEM ^c
Week 1	CHEM, CBC, UA
Week 2	CHEM, CBC, UA
Week 3	CHEM ^c
Week 4 (EOT/ET)	CHEM, CBC, UA, urine pregnancy, and urine drug screen

Abbreviations: CBC=complete blood count; CHEM=clinical chemistry serum tests; COVID-19=coronavirus disease 2019; EOT=end of treatment; ET=early termination; UA=urinalysis

^a COVID-19 diagnostic PCR test at Screening

^b Urine dipstick test will be administered which must be negative for any non-permitted medications or drugs in order for the subject to continue in the study

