^c Full chemistry (CHEM) panel of clinical laboratory tests will be completed, excluding glucose and the CHEM tests noted in [Section 6.5.5](#) to only be performed at Screening

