14.2 Clinical Laboratory Variables

Clinical laboratory tests are performed at Baseline and Week 4 (EOT/ET).

The laboratory evaluations will include, but are not limited to, the following:

- Clinical chemistry serum tests (CHEM)
 - Sodium (Na), potassium (K), chloride (Cl), phosphorus (P), calcium (Ca), carbon dioxide (CO₂), blood urea nitrogen (BUN), creatinine (CR), uric acid,
 - Estimated glomerular filtration rate (eGFR) should only be performed at Visit 1 (Screening)

- Alanine aminotransferase (ALT), aspartate aminotransferase (AST), gamma-glutamyl transpeptidase (GGT), alkaline phosphatase (ALP), total bilirubin (TBIL), lactate dehydrogenase (LDH)
 - INR to be evaluated, as needed
- Creatine kinase (CK)/creatine phosphokinase (CPK)
- Lipid panel should only be performed at Visit 1 (Screening):
 - Total cholesterol, HDL-cholesterol, triglycerides, LDL-cholesterol, cholesterol/HDL ratio, non-HDL cholesterol; should only be performed at Visit 1 (Screening)
- HbA1c should only be performed at Visit 1 (Screening)
- Glucose
- Albumin (ALB) should only be performed at Visit 1 (Screening)
- Total protein should only be performed at Visit 1 (Screening)
- Hematology tests
 - Complete blood count (CBC) including:
 - White blood cell (WBC) count
 - Complete differential (relative and absolute)
 - Hematocrit (Hct), hemoglobin, red blood cells (RBC), platelets
 - Reticulocyte count
- Endocrinology
 - Thyroid stimulating hormone (TSH) and free T4 (Screening)
- Pregnancy test
 - A serum pregnancy test should only be performed at screening for women of childbearing potential
 - A urine pregnancy test should be performed at Baseline (Week 0) and Week 4 (EOT)/ET for women of child-bearing potential
 - If urine cannot be obtained in women of childbearing potential, a serum pregnancy test should be done in its place
- COVID-19 test:

- COVID-19 diagnostic PCR test at Screening
- Urinalysis (UA)
 - Blood, RBCs, WBCs, protein, glucose, ketones, specific gravity, pH, nitrates
- Urine drug screen (UDS) with reflex testing

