 - A urine drug screen will test for controlled substances at Screening, Baseline Pain Assessment Period, and at Week 4/EOT/ET. A dipstick urine drug screen will be performed at Baseline (Week 0) for rapid detection of controlled substances and for certain prescription medications in order to determine if the subject continues to meet subject eligibility. The following controlled substances will be tested for with a urine drug screen and/or urine dipstick according to the schedule presented in Table 6–1 in protocol: amphetamine, barbiturates, benzodiazepines, buprenorphine, cocaine, ecstasy (MDMA), methadone, morphine/opiates, methamphetamine, marijuana (THC), phencyclidine (PCP), propoxyphene, tricyclic antidepressants. Negative drug screens are required for study eligibility.
 - If there is a positive urine drug screen for an analgesic medication that is not allowed per protocol, the subject must washout of medication, if appropriate, prior to the Baseline Pain Assessment Period.
 - If there is a positive urine drug screen for a medication that is allowed per protocol (e.g., metformin leading to a false positive for amphetamine), the subject must have a valid prescription for such medication, and if the subject denies use of the positive prohibited medication (e.g., amphetamine), they can be included in the study and it will not be considered a protocol deviation.

Clinical laboratory values (in Système International [SI] units) and the change from Baseline values will be summarized by treatment group at each post-Baseline visit using descriptive statistics. The overall minimum, maximum as well as the last post-Baseline observed and change from Baseline values will also be summarized. For urinalysis with categorical results, the number and percentage of subjects will be tabulated by category at Baseline and each post-Baseline visit, and the denominator is the number of subjects with non-missing values for the given parameter, visit and treatment group.

Laboratory values will also be summarized in shift tables by treatment group, to determine the number and percentage of subjects with values classified as below, within, and above normal ranges at each post-Baseline visit relative to the same classification at the Baseline

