visit. For the by-visit shift summary, the denominator is the number of subjects with non-missing values at Baseline and the given visit for the given parameter and treatment group. For the shift to the overall post-Baseline minimum or maximum, all post-Baseline values will be considered, including unscheduled and out of window values and the denominator is the number of subjects with non-missing Baseline value and at least 1 post-Baseline value for the given parameter and treatment group.

Clinical laboratory values are potentially clinically important (PCI) if they meet either the low or high PCI criteria listed in Table 2 and Table 3. The number and percentage of subjects with post-Baseline PCI values for each of the categories in Table 3 and Table 4 will be summarized by treatment group for selected parameters. For the overall post-Baseline summaries of PCI values, all post-Baseline values will be considered, including unscheduled and out of window values. Subjects with multiple PCI values for a given parameter will be counted only once for that parameter. For the overall post-Baseline summary, the numerator of the percentage is the number of subjects with at least 1 post-Baseline PCI laboratory value for the given parameter and treatment group, and the denominator is the number of subjects with at least 1 post-Baseline laboratory value for the given parameter and treatment group.

Table 2 Criteria for Potentially Clinically Important Laboratory Values – Hematology and Chemistry

Analyte	Conventional Unit	Low PCI Criteria	High PCI Criteria	SI Unit	Low PCI Criteria	High PCI Criteria
Hematology (whole blood)						
Hemoglobin (male)	g/dL	<11	>18	g/L	<110	>180
Hemoglobin (female)	g/dL	<10	>17	g/L	<100	>170
Hematocrit (male)	%	<30	>55	L/L	<0.3	>0.55
Hematocrit (female)	%	<30	>50	L/L	<0.3	>0.5
Leukocyte (White Blood Cell Count)	x 10 ³ /uL	≤2.8	≥15	x 10 ⁹ /L	≤2.8	≥15
Neutrophils	x 10 ³ /uL	≤1.5	No upper limit	x 10 ⁹ /L	≤1.5	No upper limit
Platelet Count	x 10 ³ /uL	≤75	≥700	10 ⁹ /L	≤75	≥700
Chemistry (serum or plasma)						
ALT (SGPT)	U/L	No lower limit	≥3 X ULN	U/L	No lower limit	≥3 X ULN
AST (SGOT)	U/L	No lower limit	≥3 X ULN	U/L	No lower limit	≥3 X ULN
Total Bilirubin	mg/dL	No lower limit	≥1.5 ULN	umol/L	No lower limit	≥1.5 ULN
BUN	mg/dL	No lower limit	≥30.0	mmol/L	No lower limit	≥10.71
Creatine Kinase (CK)	U/L	No lower limit	≥3 ULN	U/L	No lower limit	≥3 ULN

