- ^c A single 12-lead ECG will be performed at Screening, at Baseline (Week 0) both predose and at 1 hour postdose (the first dose of the day), Week 1, Week 2, and EOT/ET. A 1-hour window is permitted for the predose ECG and a 20-minute window is permitted for the postdose ECGs. Electrocardiograms should be performed before blood sampling or at least 30 minutes after blood sampling.
- ^d A full chemistry (CHEM) panel of clinical laboratory tests will be completed, excluding glucose and the CHEM tests noted in Section 6.5.5 to only be performed at Screening.
- ^e Applicable to women of childbearing potential. A serum pregnancy test should be performed at Screening and a urine test must be performed at all other designated visits.
- ^f At Baseline, urine drug screen will be performed using a dipstick test which must be negative for any non-permitted medications or drugs in order for the subject to continue in the study.
- ^g COVID-19 diagnostic PCR test at Screening.
- ^h Randomization visit cannot occur until there is confirmation from the central reader that there are no exclusionary findings.
- ⁱ Subjects will be instructed on the use of and will complete electronic clinical outcome assessments using handheld devices during the study. An eDiary, will be used to record pain scores, compliance with ingestion of study medication, and use of rescue medication.
- ^j A PK sample (approximately 4 mL) should also be taken from subjects who experience SAEs or AEs leading to discontinuation, as soon as possible after the occurrence of the event.
- ^k A predose PK blood sample must be collected before administration of study drug. A postdose PK blood sample will be collected at the end of ECG assessment approximately 1 hour after study drug administration.
- ^l PK samples at Visits 5, 6, and 8 will be collected at one of the following time intervals: 1) 2-5 hours after morning dosing OR 2) 6-9 hours after morning dosing OR 3) 10-12 hours after morning dosing. Every effort should be made to collect the PK samples at distinct time intervals during Visits 5, 6, and 8. However, if the interval is the same across these visits, then the collection time should vary within that interval.

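### SAP 14.2 misstates the laboratory schedule and points the by-arm laboratory PCI count at the wrong tables

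*SAP*

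**What the plan says.** **Timing.** SAP 14.2 opens with "Clinical laboratory tests are performed at Baseline and Week 4 (EOT/ET". SAP 3.2 refers the reader to Appendix A for the schedule. Appendix A marks laboratory tests at Day 3 and at Weeks 1, 2, 3 and 4, and its footnote d, attached to Day 3 and Week 3, reads "A full chemistry (CHEM) panel of clinical laboratory tests will be completed, excluding glucose and the CHEM tests noted in Section 6.5.5". Protocol 6.5.5 says "Laboratory evaluations will be completed according to the schedule presented in" Table 6-1. That table lists chemistry at the same five post-baseline visits and blood count and urinalysis at Weeks 1, 2 and 4. Its footnote c for Day 3 and Week 3 begins "Full chemistry (CHEM) panel of clinical laboratory tests will be completed, excluding glucose" and also excludes the Screening-only tests.

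**Analysis rules.** Further on, SAP 14.2 says that laboratory values and changes from Baseline "will be summarized by treatment group at each post-Baseline visit using descriptive statistics". Shift tables are planned on the same by-visit basis. The overall minimum and maximum shifts and the overall PCI summary draw on every post-baseline value, including unscheduled and out-of-window ones.

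**PCI criteria.** SAP 14.2 defines a laboratory PCI value by Tables 2 and 3. The next sentence then says that subjects with "post-Baseline PCI values for each of the categories in Table 3 and Table 4 will be summarized by treatment group", for selected parameters that it does not list. Table 2 is hematology and chemistry, Table 3 is urinalysis, and Table 4, in SAP 14.3, is vital signs. At its end, 14.2 adds a short set of extra criteria with their own flag, listing and summary: ALT, AST, GGT and ALP ≥2×ULN, and CK ≥5×ULN.

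**Stopping criteria.** Protocol 4.5.1.1 says "Discontinuation of study drug for abnormal liver tests is required by the Investigator when a subject meets one of the conditions outlined below". The conditions are ALT or AST ≥3×ULN, total bilirubin ≥1.5×ULN, and CK ≥5×ULN for more than 1 week.

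**The concern.** The schedule sentence reads as a full list of on-study laboratory visits. The matching sentences in SAP 14.4 (ECG) and 14.5 (physical examination) do list every on-study visit, so a programmer would naturally read 14.2 the same way. At Day 3 and Week 3, chemistry is the only objective safety test scheduled: vital signs, ECG and C-SSRS are not done at those visits. Those are the visits most exposed to a wrong schedule statement.

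The table reference matters more, because it sits in the sentence that plans the output. Incidence by arm against the Table 2 criteria is planned nowhere else. Table 2 holds ALT/AST ≥3×ULN and total bilirubin ≥1.5×ULN, the same thresholds that require stopping study drug under Protocol 4.5.1.1. The trial was terminated with 61 subjects randomized (SAP 1). SAP 19 reduces the secondary and exploratory efficacy analyses to description and leaves the safety plan unchanged, so laboratory safety is a large part of what the trial can still report.

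**Working it through.** No sample size, power or alpha figure is involved. The check is a count of visits and a trace of criteria.

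**Step 1. Visits named against visits scheduled** (Protocol Table 6-1; SAP Appendix A is consistent).

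| Test | Scheduled after Baseline | Number | Named in the 14.2 opening sentence | Left out |
|---|---|---|---|---|
| Chemistry | Day 3, Weeks 1, 2, 3, 4 | 5 | Week 4 (1) | 5 − 1 = 4 |
| of which glucose | Weeks 1, 2, 4 | 3 | Week 4 (1) | 3 − 1 = 2 |
| Blood count, urinalysis | Weeks 1, 2, 4 | 3 | Week 4 (1) | 3 − 1 = 2 |

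**Step 2. Does the analysis text follow the opening sentence?** It does not. Descriptive summaries and shift tables are set for each post-baseline visit, and the overall summaries take all post-baseline values. SAP 5.6.1 also brings scheduled, unscheduled and early-termination assessments into the time-point summaries. The section therefore contradicts itself, and the operative rules cover the interim visits.

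**Step 3. What is left if the PCI count uses Tables 3 and 4 as written?** All of Table 2 leaves the count. The only other laboratory threshold counts are the extra criteria at the end of 14.2.

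| Table 2 criterion | Other laboratory threshold count in 14.2 |
|---|---|
| ALT ≥3×ULN, AST ≥3×ULN | ≥2×ULN |
| ALP ≥3×ULN, GGT ≥3×ULN | ≥2×ULN |
| CK ≥3×ULN | ≥5×ULN |
| Total bilirubin ≥1.5×ULN | none |
| Hematology (hemoglobin, hematocrit, leukocytes, neutrophils, platelets) | none |
| Other chemistry (e.g. creatinine, electrolytes, LDH) | none |

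Of six liver and muscle analytes (ALT, AST, ALP, GGT, CK, total bilirubin), five keep a count at another threshold and 6 − 5 = 1, total bilirubin, keeps none. A count at ≥2×ULN includes everyone at ≥3×ULN but does not separate them, so the number of subjects per arm at the ALT/AST stopping threshold is not given by it. CK ≥5×ULN is the multiple in the protocol's CK criterion, without the duration condition.

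**Step 4. Other routes by which bilirubin is counted by arm.** Protocol 4.5.1 requires a stopping-criterion event to be recorded as an adverse event. SAP 14.1 includes the preferred terms for raised blood bilirubin and hyperbilirubinaemia among the adverse events of interest, and it tabulates TEAEs leading to discontinuation by treatment group. The shift tables count values above the normal range by arm and visit, but they use three classes (below, within, above normal) and so do not identify 1.5×ULN.

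**The case against.** The strongest reply is that both slips correct themselves. The sentence just before the wrong reference defines laboratory PCI by Tables 2 and 3, and Table 4 is titled as vital signs, so the intent is plain. The schedule sentence is descriptive preamble, while the rules that generate output refer to every post-baseline visit. Output specifications are in a separate document (SAP 1) that is not available here, so what would be programmed cannot be known. Safety is descriptive, all data are listed (SAP 5), and PCI values for a subset of chemistry, hematology and urinalysis analytes have their own listing. No endpoint or estimate changes.

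Most of this stands, and it limits what can be claimed. A reader might infer three stronger things:

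- **That laboratory tests are analyzed only at Baseline and Week 4.** The restriction to these two is not in the SAP's words, and the later rules in 14.2 contradict it.
- **That the liver and CK criteria disappear.** Five of the six analytes keep a summary at other thresholds.
- **That raised bilirubin has no count by arm.** It keeps adverse-event and shift-table counts. What it lacks is a count against the laboratory PCI threshold.

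What does not stand is the view that nothing needs changing. The count sentence is the operative one and is wrong as written. A reader can guess the intended tables, but a guess is not a prespecified rule, and a listing does not replace incidence by arm.

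**Conclusion.** Two errors in SAP 14.2 are shown by the documents.

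1. The schedule sentence conflicts with Protocol Table 6-1 and SAP Appendix A for 4 of 5 post-baseline chemistry visits and 2 of 3 blood count and urinalysis visits. The interim data remain within the analysis rules, so this is a contradiction to resolve and not a loss of data.
2. The PCI count sentence cites the wrong tables. Taken literally, the by-arm laboratory PCI count omits all of Table 2, chiefly the hematology criteria, ALT/AST ≥3×ULN and total bilirubin ≥1.5×ULN.

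The second conclusion rests on a literal reading, since the separate output specifications cannot be seen. If those specifications already use Tables 2 and 3, only the SAP text is at fault. Sample size, power, alpha and the efficacy analyses are unaffected.

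A reader might also infer that the plan is deficient because laboratory PCI has no by-visit table, unlike vital signs and ECG, or because there is no combined ALT/AST-plus-bilirubin count. The documents do not support calling either an error. Neither is promised, and Protocol 4.5.1.1 lists its criteria as separate conditions, so a combined count is not the protocol's own rule.

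**What to change.** In SAP 14.2:

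1. Replace the opening sentence with one that follows Appendix A and Protocol Table 6-1: chemistry at Baseline, Day 3 and Weeks 1, 2, 3 and 4 (EOT/ET), without glucose or the Screening-only tests at Day 3 and Week 3; blood count and urinalysis at Baseline and Weeks 1, 2 and 4 (EOT/ET). A plain cross-reference to Appendix A and Table 6-1 would also do.
2. In the PCI count sentence, change the reference to Tables 2 and 3.

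The cost is two wording changes. The data are already scheduled for collection, and the second change restores the count that the section's own PCI definition implies. If the approved SAP can no longer be revised, Protocol 9.1 already provides for deviations to be described and justified in the clinical study report.

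Optional additions, not corrections: a by-visit laboratory PCI summary in line with SAP 14.3 and 14.4, and a per-subject count of ALT or AST ≥3×ULN together with bilirubin ≥1.5×ULN. Both would add rows or tables from data already scheduled for collection.

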Systolic blood pressure (standing or sitting)	mmHg	≥180	And	Increase of ≥20
		≤90	And	Decrease of ≥20
Diastolic blood pressure (supine)	mmHg	≥105	And	Increase of ≥15
		≤50	And	Decrease of ≥15
Diastolic blood pressure (standing or sitting)	mmHg	≥105	And	Increase of ≥15
		≤50	And	Decrease of ≥15
Systolic blood pressure (supine to standing)	mmHg			Decrease ≥ 20 mmHg
Diastolic blood pressure (supine to standing)	mmHg			Decrease ≥ 10 mmHg
Pulse (supine)	bpm	≥120	And	Increase of ≥15
		≤50	And	Decrease of ≥15
				Decrease of ≥7%
Pulse (standing or sitting)	bpm	≥120	And	Increase of ≥15
		≤50	And	Decrease of ≥15
				Decrease of ≥7%

^a A post-baseline value is considered as a PCI value if it meets both criteria for observed value and change from baseline.

In addition, the following additional PCI criteria for orthostatic hypotension, significant bradycardia will be flagged, listed, and summarized:

- Orthostatic hypotension: decrease in systolic blood pressure (SBP) ≥20 mmHg or diastolic blood pressure (DBP) ≥10 mmHg after transitioning from the supine position (after resting for 5 minutes) to standing at 1 or 3 minutes with or without symptoms such as light headedness or dizziness and not explained by dehydration, illness, or medications.
- Significant bradycardia: defined as heart rate of ≤45 beats per minute (BPM) on an ECG, or pulse decrease of ≥25% from Baseline with resulting heart rate < 60 BPM.

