Electrocardiogram variable values will be considered PCI if they meet the criteria listed in [Table 5](#). The number and percentage of subjects with post-baseline PCI values will be summarized by treatment group at each post-Baseline visit and for overall post-Baseline. For the by-visit summary, the numerator for the percentage is the number of subjects with a post-Baseline PCI ECG for the given parameter, visit and treatment group, and the denominator is the number of subjects with non-missing values for the given parameter, visit and treatment group. For the overall post-Baseline summary, the numerator for the percentage is the number of subjects with at least 1 post-Baseline PCI ECG for the given parameter and treatment group, and the denominator is the number of subjects with at least 1 post-Baseline ECG value for the given parameter and treatment group. A listing of overall and of all subjects with any PCI ECG values will be provided.

Table 5 Criteria for Potentially Clinically Important ECG Values

ECG Parameter	Unit	High PCI Criteria
QRS Interval	msec	≥120
PR Interval	msec	≥220
QTcB or QTcF	msec	>500
QTcB or QTcF: change from baseline	msec	>60

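### Post-baseline PCI counts for laboratory values and for QRS, PR and absolute QTc ignore baseline status, so new and persisting abnormalities are counted together

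*SAP*

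**What the plan says.** **Laboratory values (SAP 14.2).** The definition uses fixed limits: "Clinical laboratory values are potentially clinically important (PCI) if they meet either the low or high PCI criteria listed in Table 2 and Table 3". For the overall percentage, "the numerator of the percentage is the number of subjects with at least 1 post-Baseline PCI laboratory value", and "the denominator is the number of subjects with at least 1 post-Baseline laboratory value for the given parameter and treatment group". Baseline enters neither part. The extra tiers at the end of that section (GGT and ALP at 2 x ULN, CK at 5 x ULN, among others) add no baseline condition.

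**ECG (SAP 14.4, Table 5).** "The number and percentage of subjects with post-baseline PCI values will be summarized by treatment group", and overall "the numerator for the percentage is the number of subjects with at least 1 post-Baseline PCI ECG for the given parameter and treatment group". Three of the four rows are fixed limits: QRS at least 120 msec, PR at least 220 msec, and QTcB or QTcF above 500 msec. The fourth, "QTcB or QTcF: change from baseline", is relative to baseline.

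**Vital signs (SAP 14.3, Table 4, footnote a).** Here the stated rule is two-part: "A post-baseline value is considered as a PCI value if it meets both criteria for observed value and change from baseline".

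**Adverse events (SAP 14.1).** Events that rest on pre-dose findings, including abnormal laboratory results and ECG parameters, are not treatment-emergent.

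**The concern.** PCI tables are read as lists of things that happened on treatment. Under the current rule a subject with a PR interval of 225 msec before dosing and 225 msec at Week 4 appears as a post-baseline PCI case. So does a subject whose CK was above 3 x ULN throughout. The SAP keeps a pre-dose abnormality out of the treatment-emergent adverse event tables, yet counts it in the PCI tables if it persists.

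The parameters affected include ones that the sponsor singled out: increased CK, GGT and ALP are prespecified adverse events of interest in SAP 14.1. With arms this small, one or two persisting abnormalities can produce a visible difference between arms that says nothing about the drug.

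**Working it through.** **1. Can such subjects be in the trial?** PCI limits (SAP Tables 2 and 5) set against the numeric exclusions (Protocol 4.2, criteria 14 and 16):

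| Parameter | PCI limit | Numeric eligibility limit |
|---|---|---|
| ALT, AST | at least 3 x ULN | excluded at 1.5 x ULN or more |
| Total bilirubin | at least 1.5 x ULN | excluded above ULN |
| QTcF | above 500 msec | excluded above 480 ms |
| QTcB | above 500 msec | none |
| CK, GGT, ALP | at least 3 x ULN | none |
| Uric acid | at least 10.5 mg/dL (men), 8.5 (women) | none |
| QRS, PR | at least 120, at least 220 msec | none |

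The first three rows are largely protected. The last three are exposed. BUN and glucose are partly limited by the eGFR and HbA1c criteria. Subjects on a stable statin dose may be eligible (Protocol 4.7.2).

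**2. Do other outputs separate new from persisting?** The laboratory shift tables classify by normal range, so a shift from high to high covers both a rise from 1.2 to 3 x ULN and a stable 3 x ULN. The only ECG shift table is for the cardiologist's overall interpretation. PR and QRS have summaries of values and changes by arm, which do not identify subjects. The listings allow reconstruction by hand.

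**3. Weight of one subject.** SAP section 1 gives 61 randomized; SAP 3.3 gives 1:1:1. 61/3 = 20.3 per arm. One subject is 1/20 = 5.0 points, or 1/21 = 4.8 points. The planned arm was 64/(1 - 0.20) = 80, where one subject is 1/80 = 1.25 points.

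**4. Size of the resulting noise.** The documents give no baseline prevalence, so p is an assumption, taken from 1% to 5% per parameter. Every baseline abnormality is assumed to persist, which makes the results upper bounds. Arm sizes of 20 (active) and 21 (placebo) are also assumed, since the actual split is not stated.

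Expected subjects already PCI among 61 = 61 x p.

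P(difference) = sum of Bin(x; 20, p) x Bin(y; 21, p) over all x, y with |x/20 - y/21| at least 0.0475. This threshold sits just below one subject's share in the larger arm.

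| p | 61 x p | P(difference) | active higher | placebo higher |
|---|---|---|---|---|
| 1% | 0.6 | 0.31 | 0.15 | 0.16 |
| 2% | 1.2 | 0.47 | 0.23 | 0.23 |
| 3% | 1.8 | 0.55 | 0.28 | 0.27 |
| 5% | 3.1 | 0.61 | 0.33 | 0.27 |

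The gap between the last two columns at 5% comes from the unequal denominators: one case in 20 against two in 21 is a 4.5-point difference and falls below the threshold, while two in 20 against one in 21 is 5.2 points and does not. If 1% have the abnormality and half persist, the effective p is 0.5% and P(difference) is 0.18.

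**The case against.** The strongest reply is that the SAP counts what its label says. These are post-baseline values, not treatment-emergent ones; Protocol 9.5.5 rules out formal safety testing; and under randomization stable abnormalities are symmetric noise. All of that stands. A reader might infer that the rule biases the comparison against ACP-044. It does not: the excess can fall in either arm, and no test is affected.

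Four further limits also stand.

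- It is tempting to say that no laboratory or ECG count uses baseline and that this breaks a uniform SAP rule. The QTc change row does use it. Table 4 is itself not uniform: its supine-to-standing rows and 7% pulse rows show one criterion only, and the added bradycardia flag at an ECG heart rate of 45 or below has no baseline term.
- The numeric limits are not the only filter. Exclusions 3 (which covers gout), 12 and 14 let history or clinical judgment remove some of these subjects. They reduce the number but set no threshold for the exposed parameters.
- Change summaries, normal-range shifts and PCI listings are planned, and with 61 subjects each case can be checked. Table layouts are in a separate document, so a baseline column may exist there.
- Simply dropping subjects who were PCI at baseline would be a worse rule. A QRS going from 122 to 170 msec would leave the count.

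None of this makes the planned count distinguish a new abnormality from an old one.

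**Conclusion.** The point holds as a minor improvement in reporting. As written, SAP 14.2 and 14.4 mix new and persisting PCI values for laboratory parameters and for QRS, PR and absolute QTc. The practical exposure is CK, GGT, ALP, uric acid, QRS and PR. Each persisting case is worth about 5 points in one arm, against 1.25 at the planned size. The 31-61% range rests on an assumed 1-5% prevalence, full persistence and arms of 20 and 21, so it is an upper bound for those prevalences and not an estimate. The consequence is possible misreading of descriptive tables. No efficacy result or hypothesis test changes.

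**What to change.** In SAP 14.2 (Tables 2 and 3 and the additional tiers) and SAP 14.4 (the QRS, PR and absolute QTc rows of Table 5), report the post-baseline PCI count in two parts within one table:

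- (a) New PCI: subjects with at least one post-baseline PCI value whose baseline value did not meet that limit. The denominator is the subjects not PCI at baseline for that limit who have a post-baseline value.
- (b) PCI at both times: subjects who met the limit at baseline and after it, each shown with the baseline value and the worst post-baseline value, so that worsening stays visible.

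The QTc change-from-baseline row stays as it is. While editing SAP 14.2, align the table references: the criteria are cited as Tables 2 and 3, but the summary sentence points to Tables 3 and 4, and Table 4 is vital signs.

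The cost is programming only. Baseline values are already collected, the listings are unchanged, and no value is removed from the summary.
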